#### **1.1.2. Trial registration number**

IRCT201601156135N6

### **1.2. Objectives (Description of specific objectives or hypotheses)**

Assessment of non-inferiority effect of CinnaPoietin® (Beta erythropoietin) compared with Eprex® (epoetin alpha) in correction of hemoglobin levels of anemic ESRD hemodialysis patients.

#### **Primary objective(s):**

Determination of non-inferior efficacy of Beta erythropoietin (CinnaPoietin®) compared with Eprex® (epoetin alpha) in correction of hemoglobin levels of anemic patients with chronic kidney disease (CKD) under hemodialysis

#### **Secondary objective(s):**

The secondary outcomes of interest include assessment of efficacy, safety and immunogenicity of Beta erythropoietin (CinnaPoietin®).

## **2. Section 2: Trial Methods**

### **2.1. Trial design – description of trial design (Brief description of trial design including type of trial, allocation ratio and brief description of interventions)**

The study is designed as phase III, randomized, two armed, multicenter, parallel, double blind (patient and assessor blinded), active controlled non inferiority clinical trial with primary outcome of hemoglobin level change in anemic patients with CKD under hemodialysis.

---

## **2.2. Randomization (Randomization details)**

Cluster Randomization Method will be used to randomize patients in the study. After randomization procedure, a code will be allocated to each patients that will be used as patients' identifier throughout the study.

## **2.3. Sample size (Full details of the sample size calculation or alternatively reference to sample size calculation in protocol (instead of replication in SAP))**

156 patients will be equally (1:1) divided into intervention arms (78 in each considering drop out) for achieving 80% power in order to determine non-inferiority using a one-sided, independent sample t-test. The margin of non-inferiority is -1. The true difference between the means is assumed to be -0.5. The significance level (alpha) of the test is 0.05. The data are drawn from populations with standard deviations of 1.2 and 1.2.

## **3. Section 3: Statistical Principles**

### **3.1. Confidence intervals and p-values (Level of statistical significance)**

The primary endpoints will be performed using a one-sided test with 5% significance level. All other applicable statistical tests will be 2-sided and will be performed using a 5% significance level.

### **3.2. Analysis populations (Definition of Analysis populations e.g. intention-to-treat (ITT), per-protocol, complete case, safety.)**

The primary analysis population for efficacy analyses will be the Per-Protocol (PP) population as defined below. The secondary variables will be analyzed using the ITT population. All safety analysis will be based on the safety population.

- 1- Per-protocol population. All patients who were randomized treated with study medication and did not have a major protocol deviation (to be defined before the unblinding of the database).
- 2- Modified intention-to-treat population. All patients who were randomized and received at least one dose of study medication. Patients will be analyzed according to the treatment to which they were randomized.
- 3- Safety population. All patients who were randomized and received at least one dose of study medication. Patients will be analyzed according to the treatment which they received.

### **3.3. Baseline patient characteristics**

#### **3.3.1. List of baseline characteristics to be summarized**

Patients will be described with respect to age, gender, weight, height, BMI, history of high blood pressure, and history of diabetes type 1 & 2 at baseline separately for the two randomized groups. In fact, descriptive statistics will be presented to assess the distribution of the baseline variables across treatment groups.

---

### 3.3.2. Details of how baseline characteristics will be descriptively summarized

Categorical data will be summarized by numbers and percentages. Continuous data will be summarized by mean, SD.

## 4. Section 4: Analysis

### 4.1. Outcome definitions

#### 4.1.1. Specification of outcomes and timings

Primary outcomes:

The primary efficacy endpoints will be analyzed using per-protocol (PP) analysis.

The mean Hb change level during the last four weeks of treatment is considered as the primary endpoint of the study.

The mean weekly epoetin dosage per kg body weight during the last four weeks of treatment necessary to maintain the Hb level within 10-12 g/dl during the last four weeks of treatment is considered as the second primary endpoint.

Secondary outcomes:

- The secondary variables will be analyzed using the ITT population.
- The proportion of patients with any permanent or transient dose change during main study phase is considered as the first secondary endpoint.
- The proportion of patients with any Hb measurement outside the target range is considered as the second secondary endpoint.
- The incidence of blood transfusions is considered as the third secondary endpoint.
- The proportion of patients with treatment success (Hb concentration  $\geq 11.0$  g/dl and two consecutive weeks without any blood transfusion within the preceding three months) is considered as the fourth secondary endpoint.
- The proportion of patients with maintenance success (maintenance of mean Hb concentration of  $11.0 \pm 1.0$  g/dl for at least four consecutive weeks) is considered as the fifth secondary endpoint.
- Percentage of Hb measurements  $> 10.0$  g/dl is considered as the sixth secondary endpoint.
- Percentage of hematocrit measurements  $> 30\%$  is considered as the seventh secondary endpoint.

Safety outcomes:

The incidence of Hb levels above 13 g/dl is considered as the first safety endpoint. Patients with at least one Hb measurement above 13 g/dL from week 2nd to week 26th will be taken into account to calculate this proportion.

---

The proportion of patients with an increase in Hb concentration of > 1.0 g/dl for four weeks is considered as the second safety endpoint.

Adverse events will be reported as incidence rate.

## **4.2. Analysis methods**

### **4.2.1. What analysis method will be used, and how the treatment effects will be presented**

For the primary efficacy variable, the following null hypothesis will be tested:

$H_0$ : CinnaPoietin® is not non-inferior to Eprex®

Versus

$H_1$ : CinnaPoietin® is non-inferior to Eprex®

CinnaPoietin® (produced by CinnaGen Company) efficacy will be judged non-inferior to Eprex® (the reference drug, produced by Janssen-Cilag) if the lower limit (UL) of the one-sided 95% confidence interval (95% CI) of the mean Hb change, calculated by Two Sample T-test, was more than accepted non inferiority margin.

Chi-Square test or Fisher exact test (if the expected frequencies are less than 5) will be performed for analyzing the secondary and safety outcomes.

All safety data will be analyzed descriptively by treatment group.

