
Eligibility criteria
	
Inclusion Criteria:
 
 • Aged between 18 and 70 • ESRD patients who are on hemodialysis for ≥ 3 months. • Hb level 8- 11.5 g/dl • Patients are on adequate hemodialysis: the minimally adequate dose of hemodialysis given 3 times per week should be a spKt/V (single-pool delivered Kt/V; clearance of urea x dialysis time/volume of distribution) of 1.2 per dialysis. For treatment periods of less than 5 hours, an alternative minimum dose is a urea reduction rate (URR) of 65%. All types of hemodialysis systems and hemodiafiltration, including high-flux membranes are allowed as long as there is no plan to change the patient's regimen during the study. • Sufficient iron stores, defined as serum ferritin ≥ 200 ng/ml and transferrin saturation $\geq 20\%$. (Patients not meeting these criteria may receive iron supplementation therapy during the Screening and stabilization period to appropriately correct their iron store deficiency to meet the criterion required for randomization); • Ability to comply with study medication use, study visits, and study procedures as judged by the investigator; • Females of childbearing potential agree to use an acceptable method of birth control (e.g., abstinence, hormonal or barrier methods, partner sterilization, or IUD) for the duration of the study. • Qualified and willing to sign the informed consent form with the commitment of complying with all the scheduled visits, and study procedures as judged by the investigator; • In any circumstances that potential participants are not able to give consent, it may be given by responsible parents or guardian. 
Exclusion criteria
 
 • Uncontrolled hypertension (defined as pre-dialysis diastolic blood pressure ≥ 100 mmHg or systolic blood pressure ≥ 180 mmHg); • Anemia secondary to other causes different to the CKD (e.g. multiple myeloma, aplastic anemia, leukemia....)

- Decompensated liver failure;
- Clinical evidence of concurrent uncontrolled hyperparathyroidism (defined as serum parathyroid hormone (iPTH) > 800 pg/ml);
- Heart failure [New York Heart Association (NYHA) class III and IV];
- Unstable angina pectoris, active cardiac disease, stroke and/or cardiac infarction within the last six months;
- History of or active blood coagulation disorders including DVT, PTE, native access Thrombosis during last six months.
- Thrombocytosis (platelet count > 500,000/ μ l);

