### **4.2.2. List and describe each primary and secondary outcome including details of: methods used for assumptions to be checked for statistical methods**

For analyzing the primary efficacy outcomes using independent t-tests, following assumptions should be considered:

- The dependent variable should be measured on a continuous scale
- The independent variable should consist of two categorical, independent groups.
- Observations should be independent, which means that there is no relationship between the observations in each group or between the groups themselves.
- There should be no significant outliers.
- The dependent variable should be approximately normally distributed for each group of the independent variable.
- There needs to be homogeneity of variances.

---

For analyzing the secondary efficacy and safety outcomes using Chi-square tests, following assumptions should be considered:

- The data in the cells should be frequencies, or counts of cases rather than percentages or some other transformation of the data.
- The levels (or categories) of the variables are mutually exclusive. That is, a particular subject fits into one and only one level of each of the variables.
- Each subject may contribute data to one and only one cell in the  $\chi^2$ .
- The study groups must be independent.
- There are 2 variables, and both are measured as categories, usually at the nominal level.
- The value of the cell expected should be 5 or more in at least 80% of the cells, and no cell should have an expected of less than one.

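### The primary Hb comparison makes no use of entry Hb; a pre-specified ANCOVA would cost at most about 0.3 power points and could gain several

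*SAP*

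**What the plan says.** SAP 4.2.1 declares non-inferiority from a one-sided 95% limit for the "mean Hb change, calculated by Two Sample T-test". SAP 4.2.2 lists only t-test conditions for the primary outcomes: "For analyzing the primary efficacy outcomes using independent t-tests, following assumptions should be considered". Neither document mentions a covariate, an ANCOVA or a centre term.

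SAP 2.1 describes a trial "with primary outcome of hemoglobin level change in anemic patients with CKD under hemodialysis", and SAP 4.1.1 says "The mean Hb change level during the last four weeks of treatment is considered as the primary endpoint of the study". The value from which change is measured is not named.

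The Protocol synopsis (Eligibility criteria) requires "Hb level 8- 11.5 g/dl", so an entry value exists for every eligible patient. Later Hb values are also collected: a safety endpoint in SAP 4.1.1 counts patients with "at least one Hb measurement above 13 g/dL from week 2nd to week 26th". Hb is nevertheless missing from the baseline characteristics in SAP 3.3.1.

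**The concern.** A change score subtracts baseline Hb with a fixed coefficient of 1. If the true slope of final Hb on baseline Hb is not 1, change remains correlated with baseline, and that correlation stays in the error variance. The confidence limit is then further from the estimate than it need be. ANCOVA estimates the slope instead.

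This trial is a plausible setting for a slope below 1. Patients enter at 8 to 11.5 g/dl, and the second primary endpoint concerns the dose that keeps Hb within 10 to 12 g/dl. A patient entering at 8 must gain at least 2 g/dl to reach that range, while one entering at 11.5 is already in it. This is an inference from the design, not a documented figure.

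The non-inferiority decision rests on one limit, at 80% planned power. Adjustment is credible only if it is specified before unblinding.

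**Working it through.** **Inputs.** From SAP 2.3: margin -1, assumed true difference -0.5, one-sided alpha 0.05, 80% power, 78 per arm including dropout, and "The data are drawn from populations with standard deviations of 1.2 and 1.2". Assumptions: individual randomization; change runs from entry to the last four weeks; 1.2 is the SD of that change.

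**1. The plan's own figure.** The distance from the true difference to the margin is 0.5. The normal formula gives n = 2 × 1.2² × (1.645 + 0.842)² / 0.5² = 71.2, so 72 per arm. With 72 per arm, SE = 1.2 × √(2/72) = 0.200 and the noncentrality is 0.5 / 0.200 = 2.5. Noncentral t on 142 df gives power 80.0%. The distance from estimate to limit is 1.656 × 0.200 = 0.331 g/dl. Going from 78 to 72 allows 6/78 = 7.7% dropout. The stated sample size is reproduced.

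**2. ANCOVA in terms of one unknown.** Let ρ be the correlation between baseline Hb and Hb change; only its size matters. The residual SD is 1.2 × √(1 − ρ²) on 141 df. Chance baseline imbalance inflates the variance by 141/140 on average, and power is averaged over that imbalance.

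| Size of ρ | Residual SD | Power | Estimate to limit (g/dl) |
|---|---|---|---|
| t-test, any ρ | 1.200 | 80.0% | 0.331 |
| 0 | 1.200 | 79.8% | 0.332 |
| 0.2 | 1.176 | 81.2% | 0.326 |
| 0.4 | 1.100 | 85.5% | 0.305 |
| 0.6 | 0.960 | 92.7% | 0.266 |

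ANCOVA breaks even at ρ of about 0.08.

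**3. The cost when baseline Hb explains nothing.** The loss is 0.25 points at 72 per arm (80.04% to 79.79%), 0.22 at 78, 0.29 at 65, 0.32 at 60 and 0.39 at 50.

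**4. In terms of the baseline-final correlation r.** The documents give neither r nor a baseline SD. I assume baseline SDs s_b from 0.7 to 1.01; the upper value is a uniform spread over the entry range, 3.5/√12. The final SD s_f solves s_f² + s_b² − 2·r·s_b·s_f = 1.44, and the residual variance is s_f²(1 − r²).

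| r | ANCOVA power over s_b 0.7 to 1.01 |
|---|---|
| 0.1 | 88.7 to 98.9% |
| 0.3 | 82.6 to 92.2% |
| 0.5 | 79.8 to 82.8% |
| 0.6 | 79.8 to 80.7% |
| 0.7 | 80.4 to 83.9% |

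Power is lowest where the slope r·s_f/s_b equals 1 and the change score is already the best adjustment. For example, at r = 0.3 and s_b = 1.01, s_f = 1.018 and the slope is 0.30. Then ρ = (0.3 × 1.018 − 1.01)/1.2 = −0.59, and power is 92.2%.

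**5. The same effect as imbalance.** A 1-SE chance difference in baseline Hb is s_b × √(2/72), or 0.12 to 0.17 g/dl. The change score leaves (1 − slope) of it in the estimate: 0.06 to 0.12 g/dl at r = 0.3 and 0.00 to 0.06 at r = 0.5. This is another view of the lost precision, not a further harm.

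**6. Simulation.** In six scenarios of 40,000 trials each, rejection at a true difference of -1 was 4.7 to 5.1% for the t-test and 4.8 to 5.2% for ANCOVA. At r = 0.3 and s_b = 1.01, power was 79.9% against 92.2%. At r = 0.5 and s_b = 0.7 it was 80.3% against 80.1%.

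**The case against.** The strongest objection is that nothing here is an error. The t-test is valid under individual randomization, matches the sample-size method and keeps its type I error; the gain from ANCOVA may be nil. All of that stands, and it is why this is a recommendation about efficiency.

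Other points stand in part:

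- **Meaning of change.** Read literally, the endpoint could be change within the last four weeks. Entry Hb would then not be the subtracted value, and steps 4 and 5 would lapse. Steps 2 and 3 would still hold.
- **Meaning of 1.2.** The SAP does not say what it is the SD of. If it is the SD of final Hb, the absolute powers move: at r = 0.1 the t-test has 64 to 73% and ANCOVA 80.1%; at r = 0.7 both have about 96 to 97%. ANCOVA is still no worse.
- **Extreme grid values.** The 98.9% needs a final SD of 0.76 alongside a baseline SD of 1.01, and should not be read as an expectation.
- **Size of the analysis set.** The primary set is per-protocol, with major deviations still to be defined. The 0.3-point bound is slightly exceeded at 60 per arm or fewer.
- **Clusters.** Both documents name a cluster randomization method (Protocol synopsis, Randomization; SAP 2.2), yet they give no cluster unit and describe patients as split 1:1. If clusters are randomized, neither the t-test nor a simple ANCOVA is adequate.

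**Conclusion.** The point holds as an improvement at almost no cost. At 72 evaluable per arm, ANCOVA on baseline Hb loses at most about 0.3 power points. It gains about 1, 5.5 and 13 points at correlations of 0.2, 0.4 and 0.6 between baseline Hb and Hb change. The documents do not show which of these applies.

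The absolute powers rest on individual randomization and on 1.2 being the SD of the analysed change. The small cost does not depend on what the 1.2 refers to.

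**What to change.** **SAP 4.2.1.** Replace the t-test sentence with wording such as: *The primary analysis of Hb change is an ANCOVA with treatment and baseline Hb. Non-inferiority is concluded if the lower one-sided 95% limit of the adjusted difference (CinnaPoietin minus Eprex) is above -1. The two-sample t-test is a sensitivity analysis.*

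**SAP 4.2.2.** Conform the assumptions for this endpoint and add linearity in baseline Hb. The dosage endpoint is not affected.

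**SAP 4.1.1, baseline value.** Screening runs from day -28 to 0, and "Patients not meeting these criteria may receive iron supplementation therapy during the Screening and stabilization period", so the eligibility Hb can predate iron correction. One workable rule is the last Hb before the first dose, after any screening iron correction where available, and otherwise the eligibility Hb.

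**SAP 4.1.1, endpoint visits.** State that change is from baseline, and list the visits. The Protocol's participants timeline marks Intervention up to Visit 8-2 (week 24) but not at Visit 9 (week 26, under Close-out). The final four weeks could therefore be Visits 7, 8-1 and 8-2 (weeks 20 to 24) or Visits 8-1, 8-2 and 9 (weeks 22 to 26). The sponsor must settle which. The t-test needs these two definitions as well.

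**SAP 3.3.1.** Add baseline Hb to the table.

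**SAP 2.2.** State the unit of randomization. If it is a cluster, the model must account for clustering.

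**Cost.** A few lines of SAP text, one regression command in Stata, one degree of freedom and at most about 0.3 power points. No new data are needed if the eligibility Hb serves as baseline. If a post-iron value is wanted and not already taken, one pre-dose Hb at Visit 1 is needed; the visit table has no separate Hb row.

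### The chi-square/Fisher test assigned to all secondary outcomes does not fit the sixth and seventh, which are percentages of measurements with no patient-level definition

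*SAP*

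**What the plan says.** SAP 4.2.1 gives one rule for everything other than the primary analysis: "Chi-Square test or Fisher exact test (if the expected frequencies are less than 5) will be performed for analyzing the secondary and safety outcomes". SAP 3.1 adds that "All other applicable statistical tests will be 2-sided and will be performed using a 5% significance level".

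SAP 4.1.1 lists seven secondary endpoints. The first, second, fourth and fifth are proportions of patients. The third is the incidence of transfusions, which can be read per patient. The last two have a different denominator. The percentage of Hb measurements above 10.0 g/dl "is considered as the sixth secondary endpoint", and the percentage of hematocrit measurements above 30% "is considered as the seventh secondary endpoint". Neither entry states a unit of analysis, a visit or a window. The outcomes list in the protocol synopsis words them the same way and adds nothing.

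The same SAP section shows how the detail can be given. For Hb above 13 g/dl it specifies "Patients with at least one Hb measurement above 13 g/dL from week 2nd to week 26th", which fixes both a per-patient rule and a window.

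SAP 4.2.2 lists conditions for the chi-square tests of secondary and safety outcomes. Two matter here: "Each subject may contribute data to one and only one cell in the" chi-square table, and "There are 2 variables, and both are measured as categories, usually at the nominal level". The list also requires cells to hold counts, not percentages.

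**The concern.** An analyst who follows SAP 4.2.1 to the letter has to put the sixth and seventh endpoints into a two-by-two table. The obvious table is arm by above/below threshold, with measurements as the counts. Repeated Hb values from one patient are correlated, and the test treats them as independent, so its p-values would be too small. A difference between the two products could then be reported where none exists.

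An analyst who sees that problem has to choose a unit, a window and a method that the SAP does not name, possibly after seeing data. Either way, two of the seven secondary endpoints have no workable pre-specified analysis.

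**Working it through.** **1. Does the assigned test fit any reading in the documents?**

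| Reading of endpoints 6 and 7 | SAP 4.2.2 condition | Fits? |
|---|---|---|
| All measurements pooled within arm | One cell per subject | No: a patient with several values is counted several times |
| One percentage per patient | Both variables categorical; cells hold counts | No: the outcome is a percentage |
| One yes/no result per patient | All met | Yes, but no such rule is stated for these endpoints |
| One named visit | All met | Yes, but no visit is named |

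The two readings that the wording allows both fail. The two that would work are not in the documents.

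**2. Plan figures.** The SAP gives no figure for these endpoints. Its sample size is for the primary test only and is consistent with its inputs (margin -1, true difference -0.5, SD 1.2, one-sided 5%, 80% power): n per arm = 2 × 1.2² × (1.645 + 0.842)² / (1 - 0.5)² = 71.2, so 72. The noncentral t gives 80.0% power at 72, and 78 per arm leaves room for 1 - 72/78 = 7.7% dropout. None of this depends on the secondary endpoints.

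**3. Size of the error if measurements were pooled.**

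From the documents: 78 per arm; two-sided 5%; nine visits after Visit 1 in the protocol's participants timeline (weeks 2, 4, 6, 8, 12, 20, 22, 24, 26).

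Assumed, because the documents do not give them: one value at each of those visits (the timeline has no Hb row), the within-patient correlation, and the proportion above threshold.

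Type I error = 2 × [1 - Φ(1.96/√DE)], where DE is the design effect.

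*Equal correlation between all visits, constant proportion:* DE = 1 + (m - 1) × ICC, where m is the number of values per patient and ICC the within-patient correlation.

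| ICC | DE, m = 9 | Type I, m = 9 | DE, m = 5 | Type I, m = 5 |
|---|---|---|---|---|
| 0.1 | 1.8 | 14.4% | 1.4 | 9.8% |
| 0.2 | 2.6 | 22.4% | 1.8 | 14.4% |
| 0.3 | 3.4 | 28.8% | 2.2 | 18.6% |
| 0.5 | 5.0 | 38.1% | 3.0 | 25.8% |

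With m = 9, the 78 × 9 = 702 values per arm carry the information of 702/1.8 = 390 down to 702/5.0 = 140 independent ones. A beta-binomial simulation under no difference (78 per arm, proportion 0.7 to 0.9, 20,000 runs) agreed for m = 9: 14.4% to 14.5%, 21.9% to 22.4%, 28.7% to 29.0% and 38.0% to 38.4%.

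*Correlation decaying with time:* correlation ρ at two weeks and ρ^(gap/2) at a gap in weeks, over the nine visits. DE = (1/9) × the sum of all 81 entries of the correlation matrix.

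| ρ per two weeks | Sum | DE | Type I |
|---|---|---|---|
| 0.1 | 10.31 | 1.15 | 6.7% |
| 0.2 | 11.86 | 1.32 | 8.8% |
| 0.3 | 13.71 | 1.52 | 11.2% |
| 0.5 | 18.78 | 2.09 | 17.5% |

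**4. Do patient-level methods hold their level?** In the equal-correlation simulations, over 24 settings (m = 9 and 5), type I error was 4.7% to 5.2% for a difference in mean per-patient percentage, 4.3% to 5.6% for Wilcoxon (4,000 runs), 4.8% to 5.6% for a logistic GEE clustered on patient, and 4.4% to 5.6% for chi-square on one yes/no value per patient.

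**The case against.** The best reply is that SAP 4.2.2 already rules out pooling, so an analyst who respects it could not produce the inflated error, and what remains is an incomplete endpoint definition. The first half is right: the documents do not show that pooling is planned, and the type I figures are conditional on it. But the reply confirms the conflict. Section 4.2.1 requires a test, section 4.2.2 forbids the one table that the endpoint wording supplies, and nothing provides another.

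It is also fair to say that the size is driven by assumptions. Equal correlation over 24 weeks is the less favourable case; decaying correlation roughly halves the error or better. A proportion that rises as anemia is corrected would also lower it. Both patterns leave some inflation.

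The missing window is not peculiar to these two endpoints: the second and fifth secondary endpoints have no study window either, yet they are per patient and fit the test. The window belongs in the fix but is not what makes the test unsuitable.

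A reader might infer three further things that the documents do not support:
- **That confidence intervals for these endpoints would be too narrow.** SAP 4.2.1 plans an interval only for the primary Hb change, so there is no planned secondary interval to criticise.
- **That the normality condition in SAP 4.2.2 is violated.** That condition ("The dependent variable should be approximately normally distributed for each group of the independent variable") is introduced for the t-tests of the primary outcomes and was never applied to endpoints 6 and 7.
- **That non-inferiority could be falsely claimed.** These are two-sided tests of difference, and no decision rule rests on them.

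**Conclusion.** The point holds for the sixth and seventh secondary endpoints only. The assigned test conflicts with the SAP's own conditions whether measurements are pooled or reduced to one percentage per patient, and no per-patient yes/no rule or named visit resolves it. That conclusion comes from the text alone and needs no assumption.

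The size does need assumptions. If measurements were pooled, with 9 values per patient, the nominal 5% test would have a type I error of about 14% to 38% (equal correlation 0.1 to 0.5, constant proportion) or about 7% to 18% (decaying correlation of 0.1 to 0.5 per two weeks). The documents give no correlation, proportion or Hb sampling schedule, so neither range should be read as a prediction.

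It should be corrected before unblinding, but it is a limited matter. The other secondary endpoints are not challenged here, and the primary non-inferiority analysis and the sample size stand as they are.

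**What to change.** - **SAP 4.1.1.** Define the sixth and seventh endpoints as each patient's percentage of non-missing post-baseline values above the threshold, over a stated window (for example weeks 2 to 26, as already used for Hb above 13 g/dl).
- **SAP 4.2.1.** Limit chi-square/Fisher to endpoints with one yes/no value per patient, and name one patient-level method for these two. Possible text: *For the sixth and seventh secondary endpoints, per-patient percentages will be compared between arms as a difference in means with a two-sided 95% confidence interval; a Wilcoxon rank-sum test will be reported as a check.* A logistic GEE clustered on patient would also serve if fixed in advance.
- **If the sponsor prefers to keep chi-square,** state a per-patient yes/no definition for each of the two endpoints instead.

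The cost is a few sentences in the SAP. It needs no new visits, data or patients, and no change to the primary analysis.
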